Blood and Stool Collection: Following an overnight, 12-hour fast (beginning between 8PM-12AM the day before), eligible candidates will provide a blood sample during the initial visit (baseline) and 1-month study visits. At the screening visit, eligible subjects will be provided with a stool collection kit so that they may provide a stool sample within the 18-hour period that precedes their baseline and 1-month visits. Fasting is optional for providing the stool sample.

Measurement of insulin, glucose, lipopolysaccharide (LPS) and physical function: Serum measurement of insulin and glucose are used to calculate the homeostasis model assessment (HOMA-IR), a circulating index of insulin resistance^[10]. LPS is a component of gram-negative bacterial cell walls that can appear in the blood by microbial translocation from the gastrointestinal tract^[11], is a circulating marker of metabolic endotoxemia^[12]. LPS induces insulin resistance^[12], myotube atrophy and decreased muscle function *in vitro*^[13, 14], and decreases muscle mass in rodents^[15]. Insulin, glucose and LPS will be measured by the Nutrition Evaluation Laboratory (NEL) at the Jean Mayer HNRCA at Tufts University.

[figure not shown]
Measures of physical function including the SPPB, leg press one repetition maximum (1 RM) and 400-m will be performed by the NEPS laboratory at the Jean Mayer HNRCA at Tufts University^[16]. The importance of measuring the SPPB, the leg press 1 RM and 400-m is illustrated by the finding that reduced performance in each of these measures is associated with increased disability^[1, 17, 18] and an increased all-cause mortality risk^[1, 18, 19].

Measurement of Dietary Intake: To account for the influence of dietary intake on the gut microbiome, three 24-hour dietary recalls will be collected from enrolled study subjects. Two of these recalls will be collected on the two days prior to the baseline visit. The final dietary recall will be performed on the day of the baseline visit, for a total of three 24-hour dietary recalls.

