Transplantation of gut microbiota from a healthy human adult into germ-free mice resulted in all bacterial phyla, 92% of bacterial classes and 88% of genus-level taxa being detected in the feces of recipient germ-free mice^[37]. Human gut bacteria-containing mice fed a high-fat western diet gained significantly more adiposity during the two weeks following transplantation than mice that consumed a low-fat, plant polysaccharide-rich diet^[37], evidence that demonstrates a causative role for diet-induced increases in adiposity by human gut bacteria. Similarly, transplantation of human gut microbiota from 3 twins (2 female and 1 male) discordant for obesity into germ-free mice resulted in ~75% of family-level bacterial taxa and 99.7% of the functions encoded by the donor's microbiome being represented in recipient mice, thereby resulting in a greater increase in adiposity in mice colonized with fecal microbiota from obese, when compared with its lean co-twin^[38].

Collectively, these studies demonstrate that transfer of gut bacteria from humans into germ-free mice is highly efficient, functions encoded by the transferred microbiome are maintained, and phenotypes are transmissible. The objective of **AIM 2** is to test the causative role of human gut bacteria on the maintenance of lean mass and physical function by transferring fecal microbiota from HF and LF older adults into germ-free mice.

Statistical Power: Germ-free mice colonized with fecal bacteria from obese humans gained significantly more adiposity than germ-free mice colonized with fecal bacteria from their lean co-twin ($10.0\% \pm 5.0\%$ compared with $0.1\% \pm 2.0\%$), a result that was significant 15 days after colonization^[38]. Based on these data, the resulting effect size of 2.6 is sufficient to obtain 99% power at a type-I error probability of 0.05 with a sample size of 12 human subjects. Accordingly, with the goal of identifying a similar change in lean mass and physical function, I propose to transfer fecal bacteria from 12 older adults into germ-free mice.

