III.2.a Colonization of germ-free mice with human gut bacteria from HF and LF older adults: Fecal samples from 6 HF (3 males, 3 females) and 6 LF (3 males, 3 females) older adults will be transferred into sex-matched (with the goal of minimizing sex-associated gut microbial variability^[6, 7]) C57BL/6J germ-free mice for a duration of 5 weeks at the Germ-Free and Gnotobiotic Microbiology Core at the Harvard Digestive Disease Center (HDDC; Boston, MA). The transmissible effect of host phenotype by gut microbiota has been previously reported by transferring human fecal bacteria into C57BL/6J germ-free mice^[36-38]. Furthermore, the homogenous genetic background provided by inbred C57BL/6J germ-free mice allows for a cleaner system to dissect signals from gut bacteria-host interactions, and improves experimental reproducibility, when compared with genetically heterogeneous GFM^[39]. One fecal sample from each human donor will be transferred into 5 separate germ-free mice (based on the range of germ-free mice used in human fecal transfer experiments^[36, 38]), resulting in 60 mice colonized with human gut microbiota. 5 germ-free mice will not be colonized with fecal bacteria from older adults (germ-free control group). All recipient mice will be fed *ad libitum* with a commercial, sterilized mouse chow^[38]. Food consumption will be measured daily to ensure that changes in lean mass or physical function do not result because of differences in food intake.

III.2.b Measurement and analysis of the change in lean mass and physical function in mice colonized with human gut bacteria: Lean mass and physical function in mice colonized with human gut bacteria will be measured on day 0 (prior to colonization), 9, 18, 27 and 35 days post-colonization at the HDDC. Lean mass will be measured with use of quantitative magnetic resonance imaging (EchoMRI-3in1 instrument, Houston, TX)^[38]. Muscle strength will be measured using a grip strength meter for mice (Technical and Scientific Equipment GmbH, Bad Homburg, Germany)^[40]. Each mouse will firmly grab the pulling bar of the grip strength meter with both forepaws and then pulled gently backwards until it releases its grip. The peak force of each trial is considered the grip strength. A 1-liter beaker filled with water will be used as a swimming pool to test endurance capacity^[41].

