A weight (10% of body weight) will be attached to the tail of a mouse, which is then placed in the water. The amount of time that the mouse is able to maintain complete buoyancy will be recorded. The EchoMRI, grip strength meter and beaker/weight will be sterilized prior to use to ensure that germ-free conditions at the HDDC are maintained. Because [name] has previously measured lean mass and physical function in mice^[42, 43], he will perform these measurements at the HDDC.

Differences for the change in lean mass and physical function will be calculated relative to initial values. Statistical significance for the change in lean mass and physical function will be compared in mice colonized with fecal bacteria from HF or LF human donors and for germ-free mice that were not colonized with human gut bacteria with use of two-way ANOVA^[38].

III.2.c Bacterial taxa identification and association with the change in lean mass and physical function in mice colonized with human gut bacteria: Fecal pellets will be obtained from 5 germ-free mice at baseline, which will not be colonized with human gut bacteria. Five weeks post-colonization with human gut bacteria, fecal pellets will be collected from 60 mice (30 each from the HF and LF donors) and from the 5 germ-free mice that did not receive human gut bacteria. 16S rRNA gene profiling on these 70 fecal pellets will be performed as described in **Section III.1.a**.

Associations between gut bacteria-containing principal components and individual bacterial taxa with the 35-day change in lean mass, mouse grip strength and endurance capacity will be identified as described in **Section III.1.b**. Supervised machine learning (random forest) will be used to predict whether a sample came from a mouse colonized with HF or LF donor microbiota^[44].

The gut bacterial profile that is associated with the change in lean mass and physical function in mice colonized with HF or LF human fecal bacteria is expected to be similar to the gut bacterial profile that is associated with differentiation of HF from LF older adults. CIA will be used to identify associations between circulating metabolites with gut bacteria that collectively differentiate mice colonized with HF or LF gut bacteria.

A. Subject Characteristics

1) Subject eligibility criteria:

a) Inclusion criteria:

- i) Willing and able to sign the IRB approved informed consent form
- ii) Male and Female: males, 70-85y; females, 70-80y

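### The mouse ANOVA spans HF, LF and never-colonized mice with no HF v LF contrast, so a significant group result need not mean that donor type matters

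*Protocol*

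**What the plan says.** The Aim 2 objective, in the protocol and again in the SAP, is to test a causative role of human gut bacteria on lean mass and physical function "by transferring fecal microbiota from HF and LF older adults into germ-free mice". The Statistical Power paragraph that follows uses an earlier experiment with two colonized groups, recipients of obese and of lean co-twin microbiota. It takes an effect of 2.6 SD and proposes 12 donors. No germ-free arm enters that calculation.

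Section III.2.a sets the design: "Fecal samples from 6 HF (3 males, 3 females) and 6 LF (3 males, 3 females) older adults" are the donors. "One fecal sample from each human donor will be transferred into 5 separate germ-free mice", which gives 60 colonized mice. In addition, "5 germ-free mice will not be colonized with fecal bacteria from older adults (germ-free control group").

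Section III.2.b gives the outcome: "Differences for the change in lean mass and physical function will be calculated relative to initial values". The changes are then compared in mice colonized from "HF or LF human donors and for germ-free mice that were not colonized with human gut bacteria with use of two-way ANOVA". The SAP repeats this text. Neither document names the two factors, an HF v LF contrast, a follow-up test, or which ANOVA p-value answers Aim 2. The random forest in III.2.c does separate HF from LF samples, but it classifies microbiota and does not test lean mass or function.

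**The concern.** Never-colonized mice have no donor, so they cannot be crossed with HF/LF status. Placed in the same ANOVA, they most naturally become a third level of a group factor. The null of the group term is then HF = LF = germ-free, and the null of a group-by-day term is that all three time courses are parallel. Both nulls are false whenever having any gut bacteria changes the outcome, whoever the donor was.

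The documents give some reason to allow for that. The protocol's paragraph on insulin, glucose and LPS says that LPS, a component of gram-negative bacterial cell walls, induces myotube atrophy in vitro "and decreases muscle mass in rodents". Mice with no gut bacteria lack that source.

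What is at stake is the reading of Aim 2. A significant group term could be reported as a transmissible effect of donor function when it shows only that colonized mice differ from uncolonized ones.

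**Working it through.** **Inputs.** HF 30 and LF 30 colonized mice (III.2.c: "fecal pellets will be collected from 60 mice (30 each from the HF and LF donors"); 5 never-colonized mice, 6 + 6 donors and 5 mice per donor (III.2.a); alpha 0.05 and the power figures (Aim 2 Statistical Power). The germ-free shift g, in SD units, is not in the documents and is varied.

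**1. The plan's own figure.**
- Pooled SD = √((5.0² + 2.0²)/2) = √14.5 = 3.81.
- Effect = (10.0 − 0.1)/3.81 = 2.60, as stated.
- Two-sided normal power with 6 per group = Φ(2.60 × √(6/2) − 1.96) = Φ(2.54) = 99.5%. The t-test with 10 df gives 98.1%.

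The stated 99% is thus reproduced, and it is a 6 v 6 comparison of two colonized groups.

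**2. The three-level group test when HF = LF exactly.** Assume independent mice, equal variances and one outcome. The F-test has 2 and 62 df and critical value 3.145. Its noncentrality is g² × (60 × 5)/65 = 4.615 g².

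| Assumed germ-free shift g | Noncentrality | Group test rejects |
|---|---|---|
| 0 | 0 | 5% |
| 0.25 SD | 0.29 | 7% |
| 0.5 SD | 1.15 | 14% |
| 1 SD | 4.62 | 45% |
| 1.5 SD | 10.38 | 81% |

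Simulation agrees (14%, 45% and 81% at 0.5, 1 and 1.5 SD). In the same runs the HF v LF contrast rejects about 5% of the time at every shift. The one-way group F stands in for the group main effect, because the second factor is unnamed.

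**3. What error term the contrast needs.** The 5% in step 2 assumes independent mice, but five mice share each donor. With an assumed intraclass correlation ρ, the variance of a group mean is inflated by 1 + 4ρ: 1.4, 1.8 and 2.6 for ρ = 0.1, 0.2 and 0.4. In simulation with no HF/LF difference, a mouse-level HF v LF contrast then rejects about 10%, 15% and 24% of the time. The same contrast on 6 v 6 donor means rejects about 5% in each case.

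**4. Effect on power.** At the plan's 2.6 SD, treating 6 HF donors, 6 LF donors and 5 controls as equal-variance units, the contrast has 98.7% power (14 error df). The group test has 95.8% with germ-free mice exactly midway, and 98.8% with germ-free mice equal to either group.

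**The case against.** The three-level factor is an inference, since the plan names neither factor. The plan states no decision rule and does not exclude pairwise follow-up. A reader might infer that the group p-value is the plan's declared criterion for an HF/LF effect, and so that the planned test is definitely wrong. The text does not go that far. It leaves open which p-value decides.

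The objective is also worded broadly. A causative role of human gut bacteria partly covers colonized v germ-free, and III.2.a calls the uncolonized mice a control group. That stands, but it leaves two questions sharing one undivided test, and only HF v LF is powered.

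The LPS statement says nothing about colonized v germ-free mice and gives no size. It makes a shift plausible but does not establish one. If the shift is small, so is the problem: 7% rejection at 0.25 SD.

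A reader might also infer that the germ-free arm seriously weakens the HF v LF comparison. At the plan's own effect size the loss is at most about 3 points (step 4), so power is not a reason for the change.

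Finally, this is an animal sub-experiment in a study that calls itself a pilot, and the human comparisons are unaffected.

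**Conclusion.** The concern holds in this limited form. As written, the plan compares three groups in one ANOVA with unnamed factors and no HF v LF contrast. On the natural reading, its group or group-by-day p-value answers a different question from the one powered.

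A significant result can arise with HF and LF identical. The chance ranges from 7% at a 0.25 SD germ-free shift to 81% at 1.5 SD, given independent mice, equal variances and 30/30/5. The documents do not say where in that range the truth lies, so no single false-positive rate can be attached to the plan.

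This is more than missing detail, because a better-targeted test is available from the same data. It should be settled before the mouse data are analysed.

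**What to change.** In section III.2.b of both the protocol and the SAP:

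- Name both ANOVA factors.
- State that the Aim 2 donor test is the one-degree-of-freedom HF v LF contrast among colonized mice, tested against donor-level variation, either as 6 v 6 donor means or with a random donor effect.
- Report colonized v germ-free as a separate, secondary comparison that measures the effect of colonization.
- State that a significant three-group term alone does not show an HF/LF donor effect.

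The donor-level error term is essential. Without it, the contrast can itself reject well above 5%. The cost is a few sentences of wording, with no extra mice, donors or measurements, and the germ-free group is kept.

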Bacterial taxa that differentiate HF from LF older adults: Principal co-ordinate analysis (PCoA) of the phylogeny based Unifrac distance metric^[32], which are derived from OTUs^[33] will be used to determine if the overall gut microbial profile in HF is significantly different when compared with LF older adults. The analysis of similarities function in the statistical software package PRIMER 6 (PRIMER-E Ltd., Lutton, UK^[34]) will be used to determine between-group statistical significance ($p \leq 0.05$). To identify bacterial taxa and relative abundance that are significantly different in HF when compared with LF older adults, linear discriminant analysis effect size (LEFSE)^[35] will be used. LEFSE is an algorithm for high-dimensional biomarker discovery and explanation that identifies bacterial taxa that characterize the difference between two or more biological conditions.

Test the causative role of human gut bacteria on the maintenance of lean mass and physical function: Although identification of gut bacteria that are associated with lean mass and physical function is an important observation, transplanting intact uncultured human fecal microbiota into recipient germ-free mice permits the donors' communities to be replicated and the causative role of their microbiota on outcome measures to be

discerned. For example, transplantation of human gut microbiota from 4 female twins discordant for kwashiorkor (the condition caused by severe dietary protein deficiency) into germ-free mice resulted in 86-90% of species-level taxa and ~90% of the functions encoded by the donor's microbiome being found in recipient mice, thereby implicating the gut microbiota as a causal factor on kwashiorkor^[36].

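### The mouse ANOVA names no second factor, donor term or error term, although HF/LF varies only between 12 donors; run on mice with donor ignored, it over-rejects if mice sharing a donor are correlated

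*Protocol*

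**What the plan says.** Section III.2.a takes 6 HF and 6 LF donors (3 men and 3 women in each group). "One fecal sample from each human donor will be transferred into 5 separate germ-free mice", which gives 60 colonized mice; 5 further mice stay uncolonized. Section III.2.c confirms the split: "fecal pellets will be collected from 60 mice (30 each from the HF and LF donors").

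Section III.2.b measures the colonized mice on day 0, before colonization, and on days 9, 18, 27 and 35. "Differences for the change in lean mass and physical function will be calculated relative to initial values". The instruction for testing is one sentence. It compares HF-colonized mice, LF-colonized mice and a third set, "for germ-free mice that were not colonized with human gut bacteria with use of two-way ANOVA", and supports the method with a literature citation only. The SAP text of III.2.b is the same.

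The Statistical Power paragraph for AIM 2 uses the donor as its unit: an effect size of 2.6 is said to give "99% power at a type-I error probability of 0.05 with a sample size of 12 human subjects".

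Section III.2.c adds two further analyses of the same mice. Taxa are related to the 35-day change by a method referred to Section III.1.b, a heading not visible in the supplied text. A random forest predicts whether a sample came from an HF or LF recipient, with no validation scheme stated.

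**The concern.** All 5 mice of a donor fall in the same group. Extra mice therefore sharpen the estimate for that donor but do not replicate the HF/LF contrast. If the ANOVA is run on mice with, say, sex as the second factor and donor left out, the error term contains too little between-donor variation, and the 5 mice count as 5 independent tests of HF v LF.

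The plan's own rationale implies that mice sharing a donor will be alike. Transplantation is said to allow the donors' "communities to be replicated and the causative role of their microbiota on outcome measures to be" discerned, and the AIM 2 introduction concludes that "functions encoded by the transferred microbiome are maintained, and phenotypes are transmissible". If that is right, the ICC is above 0.

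This experiment is the study's only test of causation; the human data are associational. A mouse-level analysis could report ordinary donor-to-donor differences as an effect of functional status. The same clustering bears on the taxon associations. It also bears on the random forest, which can score well by recognising donors if mice from one donor sit on both sides of a validation split.

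**Working it through.** **Inputs from the documents.** 12 donors (6 HF, 6 LF), 5 mice per donor, 30 v 30 mice (III.2.a, III.2.c); adiposity change 10.0 (SD 5.0) v 0.1 (SD 2.0), alpha 0.05, 12 human subjects (AIM 2, Statistical Power). **Assumed:** the ICC between mice of one donor, at 0, 0.05, 0.1, 0.3 and 0.5.

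**1. The plan's power figure.** d = (10.0 - 0.1)/sqrt((5.0² + 2.0²)/2) = 9.9/3.808 = 2.60. For 6 v 6 donors, the noncentral t with 10 df gives 98.1% two-sided and 99.4% one-sided; the normal approximation gives 99.5% two-sided. The stated 99% is reproduced with the donor as the unit, so the planning unit is clear.

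**2. Why a mouse-level error term is too small.** With total variance s² and ICC r, the variance of the HF - LF difference is 2s²[r/6 + (1 - r)/30] = (2s²/30)(1 + 4r). A mouse-level test works with roughly 2s²/30. The design effect is therefore 1 + 4r, and the 60 mice carry the HF/LF information of 60/(1 + 4r) independent mice.

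**3. Size of the inflation.** Simulation of 12 donors x 5 mice with no HF/LF effect, two-sided 5%, 100,000 runs for the group x sex column:

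| Assumed ICC | 1 + 4r | Equivalent mice | Group x sex on mice, donor ignored | Donor means, 6 v 6 |
|---|---|---|---|---|
| 0 | 1.0 | 60 | 5.1% | about 5% |
| 0.05 | 1.2 | 50 | 7.5% | about 5% |
| 0.1 | 1.4 | 43 | 10.1% | about 5% |
| 0.3 | 2.2 | 27 | 20.4% | about 5% |
| 0.5 | 3.0 | 20 | 29.5% | about 5% |

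The donor-mean test stayed between 4.9% and 5.1% throughout, with 10 df or with sex added (9 df). A separate simulation of 40,000 runs gave 10.0%, 20.5% and 29.9% for the group x sex test at ICC 0.1, 0.3 and 0.5.

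**4. Donor as an ordinary fixed factor.** Testing HF v LF on the within-donor error (48 df) makes matters worse: 11%, 26% and 42% at ICC 0.1, 0.3 and 0.5. Naming a donor term is not enough; the error term must be named too.

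**5. If day is the second factor.** The inputs here are shares of single-day variance, not ICCs, so these rates should not be set against the table. With donor shares of 0.1, 0.3 and 0.5, mouse shares of 0.4, 0.3 and 0.3 (all assumed) and constant donor effects, an analysis with mouse as the error stratum rejects 12.8%, 24.3% and 30.5%. Day 0 precedes colonization, so donor effects may grow over time. With linear growth to a donor share of 0.3 at day 35 and a mouse share of 0.3, a model with donor and mouse intercepts alone rejects the group x day test 11.6% of the time. A mixed model therefore also needs a donor x day effect.

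**6. Cost of the donor-level test.** At 6 v 6, 80% two-sided power needs a difference of about 1.80 donor-mean SDs (10 df), or 1.82 with sex (9 df). For a forest scored over 12 donors, one-sided binomial p is 299/4096 = 0.073 for 9 or more correct and 79/4096 = 0.019 for 10 or more, so 10 are needed to fall below 0.05.

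**The case against.** The strongest reply is that this is an unspecified model, not a wrong one. Nowhere does the plan name the mouse as the unit of analysis. The only unit it states for AIM 2 is the donor, in the power paragraph, and that figure holds up. A two-way ANOVA with donor nested in group and tested over the donor mean square would be sound, and the cited source, not available here, may describe such a model. Every error rate above depends on donor being ignored and on an ICC that the documents do not give.

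All of this stands, and it limits the claim. A reader might infer that the plan commits to analysing mice as independent units, or that the 99% power is wrong. The documents support neither reading.

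The downstream points are also softer. Whatever Section III.1.b specifies for the taxon associations cannot be judged here. How far out-of-bag accuracy would be inflated depends on the number of taxa and their clustering, for which the documents give no values; the forest point shows a mechanism and does not estimate anything for this study.

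What the reply does not remove is that an ordinary two-way ANOVA on mice also follows the sentence as written, and departs from the plan's own power unit. A citation does not settle the choice; the plan should.

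**Conclusion.** The point holds as a conditional one and should be fixed before the mouse data are analysed. The wording leaves open both a valid test and one that over-rejects. If the ANOVA is run on mice with sex as the second factor and donor ignored, the nominal 5% test rejects about 7.5% to 29.5% of the time over assumed ICCs of 0.05 to 0.5, and 5% at an ICC of 0. The plan's premise of transmissible donor phenotypes points to an ICC above 0 but does not give its size. That the model is unstated is certain; how large the inflation would be is not.

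**What to change.** State in III.2.b of both the Protocol and the SAP that the donor is the unit for HF v LF.

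- **HF v LF, each outcome.** Prespecify one summary per mouse (the day-35 change or the slope over days), average it over each donor's 5 mice, and compare 6 HF v 6 LF donor means with 10 df, or 9 df with sex.
- **Alternative using all days.** Fit a mixed model with random donor, donor x day and mouse effects and small-sample degrees of freedom.
- **Exclude** donor as a fixed factor tested on within-donor error.
- **Uncolonized mice.** They have no donor, so compare them in a separate contrast: HF and LF donor means each against the 5 control mice, allowing unequal variances (Welch).
- **Taxon associations.** Correlate taxa with the 35-day change over the 12 donor means.
- **Random forest.** Validate by holding out whole donors, for example one HF and one LF per fold, and report accuracy over 12 donors with a test that permutes donor labels.

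No extra mice or donors are needed. The price is less favourable p-values and the detectable difference of about 1.80 donor-mean SDs. A day-35 summary sets aside days 9 to 27; a slope does not. The stated 99% power becomes about 98% two-sided if the quoted SDs are taken as donor-level, an assumption the plan should state. Forest accuracy over 12 donors is a coarse measure.

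### Aim 2 mouse ANOVA: one pooled variance over 30, 30 and 5 mice can leave the germ-free comparisons, and less so the overall F, off 5%; HF v LF should be its own donor-level contrast

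*Protocol*

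**What the plan says.** Protocol section III.2.b, with the same text in the SAP, takes each mouse's change from its initial value in lean mass and physical function. It compares these changes in mice given HF or LF microbiota and "for germ-free mice that were not colonized with human gut bacteria with use of two-way ANOVA". It names neither the two factors nor the error term, and gives no variance check or unequal-variance method.

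The group sizes are in sections III.2.a and III.2.c: "fecal pellets will be collected from 60 mice (30 each from the HF and LF donors"), and "5 germ-free mice will not be colonized with fecal bacteria from older adults (germ-free control group"). The 60 colonised mice come from 6 HF and 6 LF donors, 5 mice per donor.

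The only variability figures for this experiment are in the Aim 2 power paragraph: adiposity gains of 10.0% (SD 5.0%) and 0.1% (SD 2.0%) in mice given microbiota from obese twins and their lean co-twins. The plan carries that result over to its own outcomes "with the goal of identifying a similar change in lean mass and physical function". No SD is given for lean mass, grip strength, endurance or germ-free mice.

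**The concern.** Ordinary ANOVA estimates one residual variance and uses it for every comparison. With equal group sizes that is fairly harmless when variances differ. With a 6:1 imbalance it is not. The 5 germ-free mice contribute few degrees of freedom to the pooled variance, but their own variance dominates the true error of any comparison with them. If they vary less than the pool suggests, those comparisons become very conservative; if they vary more, false positives rise.

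The plan's own planning figures differ 2.5-fold in SD (6.25-fold in variance), so equal variances cannot be taken for granted. The germ-free comparisons are what would show whether colonisation itself changes lean mass or function. HF v LF, which carries the causal question of Aim 2, is not set out as a separate contrast with its own error term.

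**Working it through.** **The plan's figure.** The standardised difference is (10.0 − 0.1)/√[(5.0² + 2.0²)/2] = 9.9/3.808 = 2.60. With 6 donors per group and two-sided 0.05, power is 99.5% by the normal formula and 98.1% by the t distribution. The stated 99% is therefore reproduced. That calculation concerns 6 v 6 donors only; the germ-free group plays no part in it.

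**Inputs for the check.** n = 30/30/5; SDs of 5 and 2 for HF and LF (exchanging them only swaps the two germ-free contrasts); germ-free SD s assumed to be 2, 3.5 or 5; no true differences; nominal two-sided 5%; mice treated as independent.

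**Why the contrasts shift.** The pooled variance has expectation (29×25 + 29×4 + 4s²)/62. This is 857/62 = 13.82, 890/62 = 14.35 or 941/62 = 15.18 for s = 2, 3.5 or 5. A contrast has true variance σa²/na + σb²/nb, but the ANOVA assigns it the pooled variance × (1/na + 1/nb). For HF v germ-free:

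- s = 2: true 25/30 + 4/5 = 1.63; assigned 13.82 × 0.2333 = 3.22; ratio 0.51.
- s = 5: true 25/30 + 25/5 = 5.83; assigned 15.18 × 0.2333 = 3.54; ratio 1.65.

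For LF v germ-free the ratios are 0.29 and 1.45. For HF v LF the true variance is 25/30 + 4/30 = 0.967 and the assigned value is 0.922 (s = 2) or 1.012 (s = 5). Those ratios are 1.05 and 0.96, so equal group sizes largely protect this contrast.

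**Simulated rejection rates, pooled analysis, 30/30/5 (200,000 runs).**

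| Germ-free SD | Overall F | HF v germ-free | LF v germ-free | HF v LF |
|---|---|---|---|---|
| 2 | 2.6% | 0.8% | 0.06% | 5.7% |
| 3.5 | 4.5% | 4.9% | 2.8% | 5.2% |
| 5 | 9.9% | 12.8% | 10.5% | 4.7% |

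A separate run of 40,000 gave 2.7% to 9.8% for the F, 0.04% to 12.5% for the germ-free contrasts and 4.6% to 5.7% for HF v LF; the differences are simulation noise. Welch contrasts on the same data reject in 4.9% to 5.9%. A group × sex ANOVA, with sex assumed as the unnamed second factor and the germ-free mice split 3/2, gives 2.5%, 4.7% and 9.9% for the group effect.

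**Donor means with germ-free mice in the same error term (6/6/5).** The pooled variance is now (5×25 + 5×4 + 4s²)/14 = 11.5, 13.9 or 17.5. The true HF v LF variance is 29/6 = 4.83; the assigned value is one third of the pooled variance, 3.83, 4.62 or 5.83. HF v LF then rejects in 9.0%, 6.1% and 3.8%, against 5.1% to 5.2% for Welch. With the germ-free mice left out (6 v 6), a pooled t-test gives 6.1% and Welch 5.1%.

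**The case against.** The strongest reply is that the main comparison is hardly touched. HF v LF at 30 v 30 stays within 4.6% to 5.7%. A reader might infer that Aim 2's causal contrast has a badly wrong error rate because of unequal variances; the figures do not support that, and this part of the reply stands.

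A reader might also quote much larger rates. An overall F near 28% and germ-free contrasts near 33% can be produced, but only by giving HF and LF equal SDs of 2 and the germ-free mice an SD of 5. That is not the plan's pattern, and no document gives a germ-free SD. At an intermediate value of 3.5 the overall F is 4.5%, close to nominal.

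Three further points stand. The SDs of 5.0 and 2.0 are adiposity figures that accompany very different means (10.0 and 0.1); spread may grow with the mean, so the ratio need not hold under the null or for lean mass, grip strength or swim time. Pooling is inferred from the name of the test, not stated. The 9% figure for HF v LF arises only if donor means and single germ-free mice share one error term, a layout the plan does not propose.

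Finally, clustering is the larger threat to HF v LF. Five mice share each donor and no donor term is named. With equal SDs and assumed within-donor correlations of 0.1, 0.3 and 0.5, treating mice as independent gives HF v LF error rates of about 10%, 19% and 27%. A Welch test on individual mice would not cure that.

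The reply leaves the germ-free contrasts exposed, and it does not supply the missing definition of the HF v LF contrast and its error term.

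**Conclusion.** The point holds in a limited form. Read as an ordinary ANOVA, the planned analysis gives unreliable error rates for comparisons with the 5 germ-free mice, with a smaller distortion of the overall F. HF v LF is near 5% at mouse level only while clustering is ignored. Moving to donors as the unit would bring in the 4% to 9% range if the germ-free mice stayed in the error term.

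The result rests on three assumptions: a pooled variance, carry-over of the 2.5-fold SD ratio to this study's outcomes, and a germ-free SD between 2 and 5. It does not show that Aim 2's main test is invalid. It is a cheap improvement that also helps with the more serious clustering problem.

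**What to change.** In section III.2.b of both documents:

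- Name HF v LF as the primary Aim 2 contrast. Test it by Welch on the 6 v 6 donor means, or by a mixed model with a donor random effect and arm-specific variances, with the germ-free mice left out of its error term.
- Make the comparisons with germ-free mice secondary, with arm-specific variances and with donor structure respected on the colonised side.
- Name the two ANOVA factors if an overall test is kept.

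The cost is wording plus some power. For HF v LF on 6 v 6 donors at the plan's means and SDs, simulated power is 97.6% pooled and 96.0% Welch. With equal variances and the same standardised difference of 2.6, it is 98.1% and 97.8%.

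The loss is larger for the germ-free contrasts, whose degrees of freedom are then limited by n = 5. With equal variances at 30 v 5 and a true difference of about 1.3 SD, power falls from about 77% to 61%. The gain can run the other way: with SDs 5/2/2 and a 3-point LF v germ-free difference, the pooled contrast detects it in 29% of runs and Welch in 72%. Both differences are illustrative.
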